3. STUDY DESIGN

The Verona Coronary Physiology Interventional Registry (VR-CP) study is a single-center, single-arm, observational study with blinded event adjudication. VR-CP enrolls patients who underwent coronary angiography for suspected ischemic heart disease, in whom at least one coronary lesion was identified and functionally assessed by coronary physiology testing (fractional flow reserve [FFR] or angiography-derived FFR).

Eligible patients are identified through registry data and review of coronary angiographic studies performed from January 2010 to December 2024. Patients meeting inclusion criteria are invited to provide written informed consent to participate in the observational study. Recruitment may occur through telephone, mail, email, or during outpatient visits. All study data are recorded in an anonymized electronic case report form (eCRF).

The follow-up involves periodic recording of the clinical status and reporting of any adverse events through review of medical records, outpatient visits, or telephone communications, in order to ensure longitudinal data collection at 12-month intervals.

Adverse events are adjudicated by an independent Clinical Event Committee (CEC) blinded to all patient clinical data. Investigators will provide the CEC with anonymized clinical documentation relating to the reported adverse event. The CEC will adjudicate events that are part of the study's primary and secondary endpoints. Event definitions and adjudication rules are established by the

Principal Investigators and recorded in the Adjudication Committee Charter. The adjudication outcomes determined by the CEC will be used for the final statistical analysis.

CEC members will be appointed by the Principal Investigator at the time of study activation. They will be selected among experienced cardiologists with no access to the clinical documentation of enrolled patients.

4. STUDY OBJECTIVES

Primary Objective

The primary objective is to identify a risk profile for vessel-oriented composite endpoint (VOCE) associated with the functional characteristics of coronary lesions documented during coronary angiography.

Secondary Objectives

Secondary objectives include:

- Assessing the prognostic value of physiological parameters (invasive FFR and angiography-derived FFR).
- Analysing the clinical, demographic, and angiographic characteristics of patients with coronary lesions evaluated by coronary physiology to identify high-risk subgroups.
- Investigating the correlation between coronary physiology values and angina symptoms.
- Comparing invasive FFR with angiography-derived FFR.
- Comparing clinical outcomes between patients managed conservatively and those undergoing invasive interventions.

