6. DESCRIPTION OF THE DISEASE IN THE STUDY

Ischemic Heart Disease and General Information on Coronary Angiography

The selection of eligible patients is based on the review of hospital registries and the analysis of coronary angiography procedures performed from January 2010 to December 2024.

Participants with suspected CAD undergo coronary angiography as part of the standard diagnostic and therapeutic pathway, in accordance with current guidelines for the management of ischemic heart disease. A patient is considered eligible if at least one mild or intermediate coronary stenosis is identified on angiographic assessment and subsequently evaluated with a coronary physiology test (fractional flow reserve [FFR] or angiography-derived FFR). These functional assessments guide the operator's decision to proceed with or defer vessel revascularization.

If a physiological evaluation of CAD is performed, the corresponding data — including FFR and/or angiography-derived FFR — are collected and recorded. The initial angiogram of all patients will be stored, anonymized, and kept locally for functional analysis (acceptable formats include CD, DVD, or digital files).

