8. PLANNED PROCEDURES AND DATA COLLECTION

The VR-CP study is a retrospective observational study enrolling consecutive patients who underwent coronary angiography for suspected ischemic heart disease and were found on angiographic examination to have coronary lesions evaluated using coronary physiology testing (FFR or angiography-derived FFR). These physiology assessments guided the decision to proceed with or defer target vessel revascularization.

Regardless of whether the lesion was treated invasively or managed conservatively, patients' clinical status and any adverse events are periodically recorded.

[figure not shown]
This retrospective follow-up is conducted through the collection of information from medical records, direct contact during outpatient visits, or via telephone communications, in order to ensure longitudinal data collection at 12-month intervals.

Fig. 1
Summary of Activities Performed

Flowchart

Fig.2 Retrospective Observational Study Design

*at the time of index procedure

DATA MANAGEMENT AND PROCEDURES TO ENSURE DATA CONFIDENTIALITY

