12. STATISTICAL ANALYSIS

Continuous variables will be tested for normal distribution using the Kolmogorov-Smirnov test.

Variables with a normal distribution will be presented as mean \pm standard deviation and compared using t-tests and one-way ANOVA. Otherwise, median [interquartile range] will be used, and comparisons will be performed using the Mann-Whitney U and Kruskal-Wallis tests. Categorical variables will be summarized as absolute and relative frequencies (percentages) and compared using the χ^2 test. Correlations between variables will be evaluated using linear and logistic regression analyses. The level of statistical significance will be set at $\alpha = 0.05$. Kaplan-Meier curves will be plotted to describe event-free survival, and differences between groups will be tested using the log-rank test. The primary analysis will be based on events occurring during the entire follow-up period for each patient at database lock. Any confounding factors will be tested using Cox regression models. Variables with a p-value < 0.1 in univariate analysis will be included in a multivariate analysis to identify independent predictors. When appropriate, 95% confidence intervals will be calculated.

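### The primary FFR–VOCE analysis combines revascularised and deferred vessels, and index management enters the Cox model only if it passes a univariate p < 0.1 screen

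*Protocol*

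**What the plan says.** Section 4 sets the primary objective as to "identify a risk profile for vessel-oriented composite endpoint (VOCE) associated with the functional characteristics of coronary lesions", without limiting it to deferred or treated vessels. Section 3 describes a "single-arm, observational study with blinded event adjudication". Section 8 says that the physiology results "guided the decision to proceed with or defer target vessel revascularization", and Section 6 likewise ties them to the operator's "decision to proceed with or defer vessel revascularization". Follow-up then covers everyone: "Regardless of whether the lesion was treated invasively or managed conservatively".

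Section 12 gives the methods. For time-to-event data, "Kaplan-Meier curves will be plotted to describe event-free survival, and differences between groups will be tested using the log-rank test"; the groups are not named. On adjustment, "Any confounding factors will be tested using Cox regression models", and variables with p below 0.1 "in univariate analysis will be included in a multivariate analysis to identify independent predictors". Index management is not named there as a covariate, a stratum or an effect modifier. Elsewhere it appears as a secondary comparison of outcomes between conservative and invasive management (Section 4) and in the antianginal-drug endpoint (Section 7).

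**The concern.** In a deferred vessel the index FFR describes a lesion that is still there. In a revascularised vessel that lesion has been treated, so the same number carries a different meaning for later events. Because the exposure steered the treatment, low-FFR vessels will be mostly treated and high-FFR vessels mostly deferred.

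Two problems follow, and they need different remedies.

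1. **Management may be left out.** Low FFR raises risk and effective treatment lowers it. In a univariate test of management the two can offset each other, p exceeds 0.1, and the rule excludes the variable most closely tied to the exposure. The FFR hazard ratio then absorbs the treatment effect.
2. **Management may be in, but with one slope.** A management main effect shifts the baseline hazard but still assumes the same FFR gradient in both groups. If the gradients differ, the common estimate lies between them.

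At stake is the primary result: the reported gradient of VOCE risk with FFR could be wrong for the deferred vessels, where the index lesion remains in place.

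**Working it through.** **The plan's own figures.** The protocol gives no FFR slope, no treated-versus-deferred hazard ratio and no model formula, so there is no stated figure to reproduce. Everything numerical below is an assumption chosen to show direction and range.

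**Assumed inputs.** 1,000 vessels, one per patient; FFR normal with mean 0.81 and SD 0.08; 90% treated at FFR ≤ 0.80 and 10% above; 20% cumulative incidence in a deferred vessel at FFR 0.80; treated-versus-deferred hazard ratio *m* at FFR 0.80 from 0.6 to 1.3. The protocol states no index treatment threshold; 0.80 appears in the introduction as a cut-off and in Section 15 as a TVR criterion.

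**Step 1: why the screen can fail.**
- P(FFR ≤ 0.80) = Φ(−0.125) = 0.450. Mean FFR is 0.740 below and 0.868 above the cut.
- Share treated = 0.9 × 0.450 + 0.1 × 0.550 = 0.460.
- Mean FFR, treated = (0.405 × 0.740 + 0.055 × 0.868) / 0.460 = 0.755.
- Mean FFR, deferred = (0.045 × 0.740 + 0.495 × 0.868) / 0.540 = 0.857.
- The difference is 0.102, or about 2.03 units of 0.05.
- With a slope of 1.30 in both groups, the univariate management hazard ratio is roughly *m* × 1.30^2.03 = 1.70*m*. At *m* = 0.6 this is 1.02: a real 40% hazard reduction looks like nothing.
- With slopes of 1.30 deferred and 1.00 treated, it is roughly *m* / 1.30^((0.80 − 0.857)/0.05) = *m* / 0.74. At *m* = 0.8 this is 1.08.
- With, say, 160 events, the standard error of the log hazard ratio is about 1/√(160 × 0.46 × 0.54) = 0.159. To reach p < 0.1 the hazard ratio must lie outside exp(±1.645 × 0.159), that is 0.77 to 1.30. Neither 1.02 nor 1.08 does.

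In simulation with *m* = 0.6–0.8, the screen dropped management in 42–85% of cohorts. A repeat with the inputs above (400 cohorts per setting, three slope patterns) gave 32–90%. The rate depends heavily on the inputs, but exclusion is common.

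**Step 2: effect on the FFR hazard ratio** (per 0.05 fall in FFR, *m* from 0.6 to 1.3):

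| True slope, deferred / treated | No management term | Management as main effect |
|---|---|---|
| 1.30 / 1.00 | 1.04–1.18 | 1.11–1.17 |
| 1.30 / 1.15 | 1.10–1.28 | 1.22–1.23 |
| 1.30 / 1.30 | 1.18–1.37 | 1.29–1.31 |

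The repeat agreed to within 0.01, and separate slopes recovered the true values. The last row shows that, with equal slopes, adjustment alone is enough. The first two show that it is not enough when slopes differ.

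**Step 3: can an interaction test decide whether to pool?** Under a second set of assumptions (FFR mean 0.82, SD 0.09, 5% crossover, N = 1,000, about 140–150 events), interaction power was 28% for true hazard ratios of 1.5 and 1.0 per 0.10 fall, and 72% for 2.0 and 1.0. A non-significant test would not justify pooling.

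**The case against.** **No one-slope model is written down.** A reader might infer that Section 12 commits to a main-effects Cox model. It does not: it gives no functional form and bars neither interactions nor stratification, the log-rank groups are undefined, and an unseen SAP may supply the detail. This stands, and silence on an interaction would not by itself be a finding. What remains is a rule the protocol does state: covariates enter on univariate p < 0.1, and management has no exemption.

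**Unequal slopes are not shown.** A reader might conclude that the hazard ratio is bound to be wrong for both groups. That needs different slopes, for which the documents give no figure; with equal slopes the adjusted estimate is valid for both. Nor does omitting management always understate the gradient: with equal slopes and *m* = 1.3 it overstates it (1.37 against 1.30). Any single-point magnitude depends on an assumed *m*.

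**A risk profile can mean prognosis under routine care.** This is a fair reading, and the protocol does not pose the causal question of what happens if a low-FFR lesion is left untreated. Even so, a prognostic description should say which vessels it describes.

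**The limitations are partly disclosed.** Section 13 admits prior clinical decisions and the lack of randomisation, but not that index FFR may relate differently to outcome after treatment.

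**Conclusion.** The concern holds in a conditional form. The documents establish that index physiology guided treatment, that both groups form one cohort for the primary objective, and that management enters the model only through a univariate screen. That screen can discard management precisely when treatment works, which biases the FFR hazard ratio even if the slopes are equal. If the slopes differ, a main effect for management does not repair the estimate: about 1.11–1.17 against true values of 1.30 and 1.00.

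These sizes rest on the assumed FFR distribution, treatment split, slopes and treated-versus-deferred hazard, none of which the protocol gives. They show that the problem can be material, not how large it will be here. It should be fixed, but it does not invalidate the study: the remedy is analytic and relies on information the registry will hold.

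**What to change.** In Section 12:

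- Include index management (deferred or revascularised) in the primary FFR–VOCE Cox model regardless of the p < 0.1 screen.
- Add an FFR-by-index-management term.
- Report FFR hazard ratios with confidence intervals, and Kaplan–Meier curves, separately for deferred and revascularised vessels, whether or not the interaction is significant.
- State the interpretation: the deferred-vessel estimate is the prognostic association of the untreated lesion, and the treated-vessel estimate is prognosis after treatment. Neither is causal.

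This costs about one paragraph and no new data collection. Each group has fewer events, so intervals widen. Deferred vessels with low FFR will be few and selected: under the assumed inputs about 45 of 1,000, with about 12 events. Confounding by indication therefore remains and should be stated as a limitation.

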5. POPULATION

Inclusion Criteria

- Previous coronary angiography with assessment of FFR and/or angiography-derived FFR.
- Age \geq 18 years old*
- Provision of written informed consent.

* At the time of the index coronary angiography.

Exclusion Criteria

- Inability to provide informed consent to participate in the study.
- Age $<$ 18 years old*

* At the time of the index coronary angiography.

Vulnerable Populations

The following subjects will not be eligible for inclusion:

- Pregnant women
- Women who are breastfeeding

Criteria for Early Withdrawal from the Study

Subject's request to withdraw participation

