1. SYNOPSIS

Study title	Verona coronary physiology interventional registry (VR-CP)
Protocol version	V1
Date	March, 1 st 2025
Study sponsor	Azienda Ospedaliera Universitaria Integrata di Verona
Study principal investigator	[name] MD PhD
Patient population	The observational Verona Coronary Physiology Interventional Registry (VR-CP) study enrolls patients with suspected coronary artery disease who underwent coronary angiography with functional assessment (coronary physiology).
Primary objective	The primary objective is to assess the functional characteristics of coronary lesions documented during coronary angiography and correlate them with the risk of cardiovascular events during follow-up.
Secondary objective	
- To examine the prognostic value of physiological parameters (FFR and angiography-derived FFR).- To analyze the clinical, demographic, and angiographic characteristics of patients with coronary lesions assessed by coronary physiology parameters, in order to identify high-risk subgroups.- To correlate coronary physiology values with angina symptoms.- To compare invasive FFR with angiography-derived FFR.- To compare clinical outcomes between patients managed conservatively and those undergoing invasive interventions.
Study design	The VR-CP study is a single-center observational study enrolling consecutive patients with coronary stenoses documented during coronary angiography and functionally assessed with coronary physiology (fractional flow reserve [FFR] or angiography-derived FFR) performed for suspected ischemic heart disease. Follow-up is conducted, after obtaining informed consent, through telephone contact and/or outpatient visits. Adverse events are adjudicated by an independent clinical events committee, blinded to clinical data.
Data source	The selection of eligible patients is extracted from registries and the analysis of coronary angiographic studies performed from January 2010 to December 2024.
Sample size	Enrollment will include approximately 1,000 patients evaluated with FFR or angiography-derived FFR. This sample size will allow for subgroup analyses stratifying lesions by functional severity based on FFR values.
Inclusion criteria	
- Coronary angiography with functional assessment by FFR or angiography-derived FFR (index procedure)- Provision of written informed consent- Age \geq18 years old at the time of the index procedure

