Exclusion Criteria	
- Inability to provide informed consent to participate in the study
Informed Consent	Patients identified as eligible for the protocol will be invited to provide informed consent for participation in the retrospective study through contact by telephone, e-mail, mail, or during an outpatient visit.
Study Procedures	Once eligibility for the protocol is confirmed, informed consent is requested and obtained. After enrolment, the angiographic images from the index coronary angiography are analysed by the investigators. Long-term follow-up is performed by monitoring the clinical status and recording major adverse cardiac events through review of medical records, outpatient visits, or telephone contacts.
Primary Endpoint	Composite of vessel-oriented composite endpoint (VOCE), including target vessel revascularization (TVR), target vessel-related myocardial infarction (MI), and cardiovascular death.
Secondary Endpoints	
- Individual components of the primary endpoint- Hospitalization for unstable angina- Angina status (Seattle Angina Questionnaire)- Number of prescribed antianginal medications
Study Duration	Patients are retrospectively enrolled from January 2010 to December 2024. Clinical contact (medical records, outpatient visits, telephone communication) is periodically collected recording longitudinal data at 12-month intervals.
Clinical Event Adjudication Committee	The following events are adjudicated by an independent committee blinded to clinical data: TVR, target vessel-related MI, cardiovascular death, and hospitalization for unstable angina.

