7. ENDPOINTS

Primary Endpoint

The primary endpoint is the composite risk of vessel-oriented composite endpoint (VOCE), including target vessel revascularization (TVR), vessel-related myocardial infarction (MI), and cardiovascular death.

Secondary Endpoint

- Individual components of the primary endpoint.
- Hospitalization for unstable angina.
- Angina status assessed using the Seattle Angina Questionnaire (SAQ). The SAQ will be used to evaluate patients' quality of life and the impact of angina symptoms over time. Scores from the main subscales (physical limitation, angina stability, angina frequency, treatment perception, and overall quality of life) will be analysed to correlate symptom severity with coronary physiology parameters (e.g., FFR/angiography-derived FFR).
- Number of prescribed antianginal drugs. The number of prescribed antianginal medications will be monitored to assess the intensity of pharmacological treatment required during follow-up. This parameter will serve as a proxy for residual disease severity and will allow comparison between patients managed conservatively and those treated with invasive interventions.

[figure not shown]

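### Section 13 says consecutive enrolment minimizes selection bias, but only patients alive to consent can enter, so recorded cardiovascular deaths before consent are zero by construction

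*Protocol*

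**What the plan says.** **Who enters.** Synopsis, Data source: "The selection of eligible patients is extracted from registries and the analysis of coronary angiographic studies performed from January 2010 to December 2024". Synopsis, Informed Consent: "Patients identified as eligible for the protocol will be invited to provide informed consent for participation in the retrospective study". Section 3 repeats it: "Patients meeting inclusion criteria are invited to provide written informed consent to participate in the observational study". Section 5 makes written consent an inclusion criterion and lists as an exclusion "Inability to provide informed consent to participate in the study". The data-confidentiality section has consent obtained from the patient before enrolment, and Section 10 gives the order as eligibility, consent, enrolment. Version 1 is dated 1 March 2025.

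**What is measured.** The Section 7 primary endpoint is the vessel-oriented composite (VOCE), "including target vessel revascularization (TVR), vessel-related myocardial infarction (MI), and cardiovascular death". The secondary endpoints begin with "Individual components of the primary endpoint", so CV death also stands alone. Section 4 frames the primary objective as an association: "The primary objective is to identify a risk profile for vessel-oriented composite endpoint (VOCE) associated with the functional characteristics of coronary lesions".

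**How it is analysed.** Section 12 plans Kaplan-Meier curves, log-rank tests and Cox models on all events in each patient's follow-up to database lock. Section 8 calls the follow-up retrospective, and Section 10 carries it to a 10-year evaluation. The Synopsis puts it differently: "Follow-up is conducted, after obtaining informed consent, through telephone contact and/or outpatient visits".

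**What is claimed.** Section 13 concedes that retrospective enrolment may introduce selection bias, through limited representativeness and earlier clinical decisions. It then offers consecutive enrolment as the remedy, says that this minimizes the bias, and gives as its goal a sample like the patients seen in routine practice.

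**The concern.** Consecutive screening of angiograms does not give consecutive enrolment when the dead and the untraceable cannot enter. Every enrolled patient is known to have survived from index to consent, a gap that can exceed 15 years for the earliest procedures. Over that interval the data hold no CV deaths, whatever the true rate. Non-fatal revascularization and infarction in survivors can still be recovered from records, so the composite is thinned selectively: its fatal part is lost and its non-fatal part in survivors is kept.

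At stake are the absolute risks, the make-up of the composite and the claim of representativeness. A reader relying on Section 13 would take the event-free survival curves as those of an ordinary patient population.

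**Working it through.** **1. The structural step needs no rates.** Consent comes from the patient and precedes enrolment, so enrolled implies alive at consent, and CV deaths between index and consent number 0. The consent start is inferred from the protocol date. A later start lengthens the gap.

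**2. Time origin.** It is not stated. Sections 8, 10 and 12 (retrospective follow-up, 10-year evaluation, entire follow-up) read most naturally as time from index, while the Synopsis sentence on follow-up points to consent. From index, the curves contain death-free time by construction. From consent, they do not, but the cohort is still selected survivors. The Section 13 claim fails either way.

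**3. Inputs for size.** The protocol has no figure to reproduce here: it gives no mortality rate and no calendar distribution. Assumed: CV death a = 1% or 2% per year; non-CV death b = 1.5%; non-fatal VOCE c = 3%; constant independent hazards; non-fatal events not changing mortality; consent spread evenly over April-December 2025; index dates spread evenly over 2010-2024 or 2020-2024; lock at end 2034 (10 years after the last index procedure).

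**4. Risk with no selection.** Kaplan-Meier with non-CV death censored gives 1 − exp(−10a) = 9.5%/18.1% for CV death and 1 − exp(−10(a+c)) = 33.0%/39.3% for VOCE. These are not absolute risks. With non-CV death as a competing event:
- CV death: a/(a+b) × [1 − exp(−10(a+b))] = 0.400 × 0.2212 = 8.8% and 0.571 × 0.2953 = 16.9%.
- VOCE: (a+c)/(a+b+c) × [1 − exp(−10(a+b+c))] = 30.8% and 36.8%.

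**5. What an ordinary curve from index shows.** Let G be the gap from index to consent and h = a + b. At time t the at-risk set holds patients past consent, A(t) = P(G ≤ t)·exp(−ht), and patients not yet at consent who cannot die before it, B(t) = E[exp(−hG); G > t]. The CV-death hazard seen is a·A/(A+B).

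Example for index 2010-2024, a = 1%, t = 5, consent at its mean date: P(G ≤ 5) = 4.375/15 = 0.292; A = 0.292 × exp(−0.125) = 0.257; B = [exp(−0.125) − exp(−0.3906)]/(15 × 0.025) = 0.549. The hazard seen is 0.01 × 0.257/0.806 = 0.0032, a third of the true 0.01. Integrated over 10 years it is 0.0313, and 1 − exp(−0.0313) = 3.1%.

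The share of 10-year CV deaths falling before consent is E[1 − exp(−h·min(G,10))]/[1 − exp(−10h)].

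| Quantity (a = 1% / 2%) | No selection | Index 2010-2024 | Index 2020-2024 |
|---|---|---|---|
| Mean gap, years | – | 8.1 | 3.1 |
| 10-year CV deaths before consent | – | 72% / 73% | 34% / 35% |
| 10-year CV death, Kaplan-Meier | 9.5% / 18.1% | 3.1% / 6.2% | 6.7% / 12.9% |
| 10-year VOCE, Kaplan-Meier | 33.0% / 39.3% | 28.2% / 30.5% | 30.9% / 35.5% |
| CV death among first VOCE events, to lock | 25% / 40% | 13.5% / 23.7% | 18.9% / 31.5% |

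**6. The association.** Simulated VOCE Cox hazard ratios for low against high FFR (a = 2%, 40% of patients low), full cohort to survivors only:

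| True HR, non-fatal / fatal | Index 2010-2024 | Index 2020-2024 |
|---|---|---|
| 1.5 / 1.5 | 1.50 to 1.50 | 1.50 to 1.50 |
| 1.5 / 2.0 | 1.70 to 1.62 | 1.70 to 1.66 |
| 2.0 / 1.5 | 1.80 to 1.89 | 1.80 to 1.85 |
| 1.0 / 2.0 | 1.40 to 1.25 | 1.40 to 1.32 |
| 2.0 / 1.0 | 1.60 to 1.77 | 1.60 to 1.69 |

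Equal effects give no shift only while non-fatal events leave mortality alone. If they triple later CV mortality (assumed, index 2010-2024), 1.50 becomes 1.48 and 3.0 becomes about 2.85. Delayed-entry Cox returned the full-cohort value to within 0.01 in the tabulated settings.

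**The case against.** The primary objective is an association, no stated objective is to estimate absolute CV mortality, and the association moves little. That stands, and it limits the severity. A reader might infer that the main FFR result is invalid. The documents do not support this: the planned Cox model remains usable, and any shift is modest unless the effects on fatal and non-fatal events differ widely.

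Section 13 is also not silent. It names selection bias and adds that historical practice limits generalizability, so a charge that the bias goes unmentioned would be unfair. The fault is narrower: the remedy does not address survival to consent or contact for it, and the conclusion drawn from it is false.

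Time origin and delayed entry are often left to a statistical analysis plan, and Section 12 does not say that curves start at index. This is fair, and their absence is not the finding. They enter because Section 12's ordinary curves, read naturally, would understate risk. The Section 13 statement is wrong whatever an analysis plan adds.

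Finally, every rate and calendar above is assumed. The direction under an index origin is the same in each scenario; only the size varies.

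**Conclusion.** The point holds. The incorrect statement is in Section 13; the consent criterion in Section 5 is its cause and need not itself change. Enrolment is conditional on survival to, and contact for, consent, and recorded CV deaths before consent are zero by construction.

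If time runs from index, ordinary Kaplan-Meier curves understate CV death substantially, VOCE less so, and the share of death in the composite. Under the assumed rates, 10-year CV death reads roughly a third of its value for index 2010-2024 and roughly 70% of it for 2020-2024. If time runs from consent, that distortion disappears but the claim of representativeness still fails.

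The VOCE hazard ratio is nearly unchanged if physiology acts equally on fatal and non-fatal events and non-fatal events do not much alter mortality. Otherwise it shifts in either direction. This should be fixed, but it does not undermine the primary objective.

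**What to change.** 1. **Section 13.** Replace the claim that consecutive enrolment minimizes selection bias with a statement that enrolment is conditional on survival to, and contact for, consent. Report the flow of all eligible 2010-2024 patients: consented, declined, dead, untraceable. The cost is wording and a count.

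2. **Section 12.** State the index procedure as time origin. Estimate absolute CV-death and VOCE risk with delayed entry at consent (for VOCE, among patients event-free at consent) and with non-CV death as a competing event. Start each curve where a stated minimum number is at risk, and present it as conditional on being event-free then. State the assumption that consent is unrelated to prognosis; if it is not, bias remains. Do not present ordinary curves from index as absolute risk. Keep the planned Cox model for the association and add a delayed-entry Cox as a sensitivity analysis.

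   The cost is precision in the absolute-risk curves and the sensitivity Cox only. Under the assumed rates, usable first VOCE events to lock per 1,000 consenting patients fall from 434 to 235 (46%) or 477 to 282 (41%) for index 2010-2024, and from 354 to 267 (25%) or 408 to 321 (21%) for 2020-2024. For CV death, about 30 per 1,000 are at risk at 1 year and about 110 at 2 years (2010-2024), or about 80 and 285 (2020-2024), so curves would start near year 2.

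3. **Optional.** Include deceased patients from records, only if the ethics committee allows it and vital status and cause of death can be obtained for all eligible patients, including the untraceable.
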